8.1 Efficacy Assessments

Not applicable.

8.2 Safety Assessments

Planned timepoints for all safety assessments are provided in Section 1.3.

8.2.1 Physical Examinations

- Physical examination of the subject, including assessment of oral body temperature.
- Collected information needs to be recorded in the eCRF.
- If the Investigator determines that the subject's health on the day of vaccination temporarily precludes vaccination, the visit will be rescheduled within the protocol visit window.
- Treatment of any abnormality observed during this examination has to be performed according to local medical practice outside this study or by referral to an appropriate health care provider.

8.2.2 Vital Signs

- Resting vital signs: systolic/diastolic blood pressure and heart rate after at least 10 minutes of rest.
- Vital signs are to be taken before blood collection for laboratory tests and will consist of 1 pulse and 1 blood pressure measurement.
- Blood pressure and pulse measurements will be assessed with a completely automated device. Manual techniques will be used only if an automated device is not available.
- Collected information needs to be recorded in the eCRF.

8.2.3 Clinical Safety Laboratory Assessments

Approximately 5.5 mL of blood for hematology and biochemical analysis and approximately 10 mL of urine for urinalysis will be collected from all subjects at the timepoints specified in Section 1.3.

Please refer to [Appendix 4](#) for a detailed description of the assays performed in the study. Please refer to [Appendix 5](#) for the address of the clinical laboratories used for sample analysis.

Hematology, biochemistry, and urine assessments will be performed in the Investigator's laboratory as per local practice using standardized and validated procedures ([Appendix 4](#)).

- The Investigator must review the laboratory report, document this review, and record any clinically relevant changes occurring during the study in the AE section of the eCRF. The laboratory reports must be filed with the source documents. Clinically significant abnormal laboratory findings are those which are not associated with an underlying disease, unless judged by the Investigator to be more severe than expected for the subject's condition.
- All laboratory tests with values considered clinically significant abnormal during participation in the study or within 30 days after the last dose of study treatment should be repeated until the values return to normal or baseline or are no longer considered significantly abnormal by the Investigator or Medical Monitor. Refer to [Appendix 6](#) for clinical laboratory abnormal assessments qualified as AEs or SAEs.
- If such values do not return to normal/baseline within a period of time judged reasonable by the Investigator, the etiology should be identified, and the Sponsor notified.
- All protocol-required laboratory safety assessments, as defined in [Appendix 4](#), must be conducted in accordance with the laboratory manual and Section 1.3.

8.3 Adverse Events

Please refer to [Appendix 6](#) for safety definitions.

Adverse events will be reported by the subject (or, when appropriate, by a caregiver, surrogate, or the participant's legally authorized representative) or identified at the study visit.

The Investigator and any designees are responsible for detecting, documenting, and recording events that meet the definition of an AE or SAE and remain responsible for following up AEs that are serious, considered related to the study treatment or study procedures, or that caused the subject to discontinue the study treatment (see Section [7.0](#)).

An overview of the protocol-required reporting periods for AEs, SAEs, AEs of specific interest, and pregnancies is given in [Table 17](#).

Table 17 Reporting Periods for Collecting Safety Information

	Screening	Visit 1		Visit 2		Visit 3		Visit 4		Visit 5	Visit 6	Visit 7	Screening for Dose 3	Visit 8 for Step 4	Visit 9 for Step 4	Visit 10 for Step 4	Visit 11 for Step 4
		D1	D7	D8	D30	D31	D37	D38	D60	D61	D180	D390	D476	D491	D498	D521	D670
Solicited local and general AEs																	
Unsolicited AEs																	
SAEs (all, fatal, related to study vaccine)																	
SAEs related to study participation or concurrent GSK medication/vaccine																	
Pregnancies																	
AEs of specific interest (pIMDs)																	

AE = adverse event; D = day; GSK = GlaxoSmithKline Biologicals SA; pIMDs = potential immune-mediated diseases; SAE = serious adverse event

8.3.1 Time Period and Frequency for Collecting Adverse Event and Serious Adverse Event Information

All AEs and SAEs will be collected from the signing of the ICF until the Follow-up Visit at the timepoints specified in Section 1.3.

Medical occurrences that begin before the start of study treatment but after obtaining informed consent will be recorded on the Medical History/Current Medical Conditions section of the eCRF, not the AE section.

All SAEs will be recorded and reported via Expedited AE Reporting Form to the Sponsor or designee immediately and under no circumstance should this exceed 24 hours after the Investigator became aware of it, as indicated in [Appendix 6](#). The Investigator will submit any updated SAE data to the Sponsor within 24 hours of it being available.

A poststudy AE/SAE is defined as any event that occurs outside of the AE/SAE reporting period defined in [Table 17](#). Investigators are not obligated to actively seek AEs or SAEs in former study subjects. However, if the Investigator learns of any SAE, including a death, at any time after a subject has been discharged from the study, and he/she considers the event to be reasonably related to the study vaccine(s), the Investigator will promptly notify the Study Contact for Reporting SAEs.

Refer to [Appendix 6](#) for local (injection site) and general solicited AEs to be collected.

At each vaccination visit, paper diary cards will be provided to the subject. The subject will be instructed to measure and record the oral body temperature, and any solicited local/general AEs (ie, on the day of vaccination and during the next 6 days) or any unsolicited AEs (ie, on the day of vaccination and during the next 30 days) occurring after vaccination. The subject will be instructed to return the completed diary card to the Investigator at the next study visit.

Adverse events of specific interest (AESIs) for safety monitoring include pIMDs (refer to [Appendix 2](#) for definition of pIMD). Adverse events that need to be recorded and reported as pIMDs include those listed in [Table 18](#).

Table 18 List of Potential Immune-mediated Diseases

Neuroinflammatory disorders	Musculoskeletal disorders	Skin disorders

 • Cranial nerve neuropathy, including paralysis and paresis (eg, Bell's palsy). • Optic neuritis. • Multiple sclerosis. • Transverse myelitis. • Guillain-Barré syndrome, including Miller Fisher syndrome and other variants. • Acute disseminated encephalomyelitis, including site specific variants, eg, noninfectious encephalitis, encephalomyelitis, myelitis, myeloradiculoneuritis. • Myasthenia gravis, including Lambert-Eaton myasthenic syndrome. • Demyelinating peripheral neuropathies including: 
 - Chronic inflammatory demyelinating polyneuropathy. - Multifocal motor neuropathy. - Polyneuropathies associated with monoclonal gammopathy. • Narcolepsy. 	
 • Systemic lupus erythematosus and associated conditions. • Systemic scleroderma (systemic sclerosis), including: 
 - Diffuse scleroderma. - CREST syndrome. • Idiopathic inflammatory myopathies, including: 
 - Dermatomyositis. - Polymyositis. • Antisynthetase syndrome. • Rheumatoid arthritis and associated conditions including: 
 - Juvenile idiopathic arthritis. - Still's disease. • Polymyalgia rheumatica. • Spondyloarthropathies, including: 
 - Ankylosing spondylitis. - Reactive arthritis (Reiter's syndrome). - Undifferentiated spondyloarthritis. - Psoriatic arthritis. - Enteropathic arthritis. • Relapsing polychondritis. • Mixed connective tissue disorder. • Gout. 	
 • Psoriasis. • Vitiligo. • Erythema nodosum. • Autoimmune bullous skin diseases (including pemphigus, pemphigoid, and dermatitis herpetiformis). • Lichen planus. • Sweet's syndrome. • Localized scleroderma (morphea).
Vasculitis 
 • Large vessels vasculitis including: 
 - Giant cell arteritis (temporal arteritis). - Takayasu's arteritis. • Medium sized and/or small vessels vasculitis including: 
 - Polyarteritis nodosa. - Kawasaki's disease. - Microscopic polyangiitis. - Wegener's granulomatosis (granulomatosis with polyangiitis). - Churg-Strauss syndrome (allergic granulomatous 	Blood disorders 
 • Autoimmune hemolytic anemia. • Autoimmune thrombocytopenia. • Antiphospholipid syndrome. • Pernicious anemia. • Autoimmune aplastic anemia. • Autoimmune neutropenia. • Autoimmune pancytopenia. 	Others 
 • Autoimmune glomerulonephritis including: 
 - IgA nephropathy. - Glomerulonephritis rapidly progressive. - Membranous glomerulonephritis. - Membranoproliferative glomerulonephritis. - Mesangioproliferative glomerulonephritis. - Tubulointerstitial nephritis and uveitis syndrome. • Ocular autoimmune diseases including: 
 - Autoimmune uveitis.

Table 18 List of Potential Immune-mediated Diseases

angiitis or eosinophilic granulomatosis with polyangiitis).
 
 - Buerger's disease (thromboangiitis obliterans). - Necrotizing vasculitis (cutaneous or systemic). - Antineutrophil cytoplasmic antibody positive vasculitis (type unspecified). - Henoch-Schonlein purpura (IgA vasculitis). - Behcet's syndrome. - Leukocytoclastic vasculitis. 		
 - Autoimmune retinitis. • Autoimmune myocarditis. • Sarcoidosis. • Stevens-Johnson syndrome. • Sjögren's syndrome. • Alopecia areata. • Idiopathic pulmonary fibrosis. • Goodpasture syndrome. • Raynaud's phenomenon.
Liver disorders	Gastrointestinal disorders	Endocrine disorders

 • Autoimmune hepatitis. • Primary biliary cirrhosis. • Primary sclerosing cholangitis. • Autoimmune cholangitis. 	
 • Inflammatory bowel disease, including: 
 - Crohn's disease. - Ulcerative colitis. - Microscopic colitis. - Ulcerative proctitis. • Celiac disease. • Autoimmune pancreatitis. 	
 • Autoimmune thyroiditis (Hashimoto thyroiditis). • Grave's or Basedow's disease. • Diabetes mellitus type 1. • Addison's disease. • Polyglandular autoimmune syndrome. • Autoimmune hypophysitis.

IgA = immunoglobulin A

8.3.2 Method of Detecting Adverse Events and Serious Adverse Events

The method of recording, evaluating, and assessing intensity, causality and outcome of AEs and SAEs and the procedures for completing and transmitting SAE reports are provided in [Appendix 6](#).

Care will be taken not to introduce bias when detecting AE and/or SAE. Open-ended and nonleading verbal questioning of the subjects is the preferred method to inquire about AE occurrence.

8.3.3 Follow-up of Adverse Events and Serious Adverse Events

After the initial AE/SAE report, the Investigator is required to proactively follow each subject at subsequent visits. All SAEs and AESIs will be followed until the event is resolved, stabilized, otherwise explained, or the subject is lost to follow-up. Further information on follow-up procedures is given in [Appendix 6](#).

8.3.4 Treatment of Adverse Events

Treatment of any AE is at the sole discretion of the Investigator and according to current good medical practice. Any medication administered for the treatment of an SAE/AESIs should be recorded in Expedited Adverse Event Report of the subject's eCRF (refer to Section [6.8](#)).

8.3.5 Regulatory Reporting Requirements for Serious Adverse Events

- Prompt notification of an SAE by the Investigator to the Sponsor is essential for meeting legal obligations and ethical responsibilities for the safety of subjects and the safety of a study treatment under clinical investigation.
- The Sponsor has a legal responsibility to notify both the local regulatory authority and other regulatory agencies about the safety of a study treatment under clinical investigation. The Sponsor will comply with country-specific regulatory requirements relating to safety reporting to the regulatory authority, IRB/IEC, and Investigators.
- Investigator safety reports must be prepared for SUSARs according to local regulatory requirements and Sponsor policy and forwarded to Investigators as necessary.
- An Investigator who receives an Investigator safety report describing an SAE or other specific safety information (eg, summary or listing of SAE) from the Sponsor will review and then file it along with the IB and will notify the IRB/IEC, if appropriate according to local requirements.

8.3.6 Pregnancy

Female subjects of childbearing potential are to have a urine pregnancy test prior to any study vaccine administration. The study vaccine(s) may only be administered if the pregnancy test is negative.

Note: Pregnancy test must be performed even if the subject is menstruating at the time of the study visit.

See [Appendix 7](#) for collection of pregnancy information.

8.4 Treatment of Overdose

Not applicable.

8.5 Pharmacokinetics

Not applicable.

8.6 Pharmacodynamics

Not applicable.

8.7 Genetics

Genetics are not evaluated in this study.

8.8 Immunogenicity Assessment

Blood Sampling for Immunogenicity Response Assessments

All subjects from Steps 1, 2, 3, and 4

A volume of approximately 20 mL of whole blood should be drawn for analysis of humoral immune response at each predefined timepoint specified in Section 1.3. After centrifugation, serum samples should be kept at -20°C or below until shipment. Refer to the SPM for more details on sample storage conditions.

Subjects from Step 4 who consented for the additional sampling

For subjects who agreed to the optional blood sampling, a volume of approximately 40 mL of whole blood should be drawn for peripheral blood mononuclear cell (PBMC) isolation on Day 61 (Visit 5; refer to the schedule of activities in Section 1.3) and may be used for generation of monoclonal antibodies. The blood should be kept at the study center at a constant room temperature and it must not be centrifuged. Samples will be shipped at a constant room temperature (15 to 25°C) to the designated laboratory for PBMC separation to be performed within 18 hours.

Refer to the SPM for more details on sample storage conditions.

Monoclonal antibodies may be generated using the samples collected during the study and used for further research purposes as well as commercial use.

Information on further investigations and their rationale can be obtained from GSK.

Any sample testing will be done in line with the consent of the individual subject.

8.8.1 Laboratory Assays

Please refer to [Appendix 5](#) for the address of the clinical laboratories used for sample analysis.

- Anti-Toxin A and anti-Toxin B neutralizing antibody titers will be measured by toxin neutralization assay (TNA) on serum samples, using different cell lines, at a GSK laboratory or in a laboratory designated by GSK using standardized and validated procedures ([Table 20](#)).
- Anti-Toxin A and anti-Toxin B antibodies concentrations will be determined by enzyme-linked immunosorbent assay on serum sample at a GSK laboratory or in a laboratory designated by GSK using standardized and validated procedures ([Table 20](#)).

Table 20 **Humoral Immunity (Antibody Determination)**

System	Component	Method	Laboratory	
Serum	Anti-Toxin A neutralizing antibodies (different cell lines)	TNA	GSK ^a or designated laboratory	
	Anti-Toxin B neutralizing antibodies (different cell lines)			
	Anti-Toxin A IgG	ELISA		
	Anti-Toxin B IgG			

ELISA = enzyme-linked immunosorbent assay; GSK = GlaxoSmithKline Biologicals SA;

IgG = immunoglobulin G; TNA = toxin neutralization assay.

^a GSK laboratory refers to the Clinical Laboratory Sciences in Rixensart, Belgium, and Wavre, Belgium.

Additional testing on the vaccine and/or on the disease under study may be performed within the framework of the study if deemed necessary for accurate interpretation of the data or should such assay(s) become available at GSK. These assays may not be represented in the objectives/endpoints of the study protocol.

The GSK clinical laboratories have established a Quality System supported by procedures. The activities of GSK clinical laboratories are audited regularly for quality assessment by an internal (Sponsor-dependent) but laboratory-independent Quality Department.

8.8.2 Immunological Read-outs

In case of insufficient blood sample volume to perform assays for all antibodies, the samples will be analyzed according to priority ranking provided in [Table 21](#).

Table 21 Immunological Read-outs

Blood Sampling Timepoint	Number of Subjects	Component	Components Priority Rank
Type of Contact and Timepoint			
Visit 1 (Day 1)	~140	Anti-Toxin B neutralizing antibodies	1
		Anti-Toxin A neutralizing antibodies	2
		Anti-Toxin B immunoglobulin G	3
		Anti-Toxin A immunoglobulin G	4
Visit 3 (Day 31)	~140	Anti-Toxin B neutralizing antibodies	1
		Anti-Toxin A neutralizing antibodies	2
		Anti-Toxin B immunoglobulin G	3
		Anti-Toxin A immunoglobulin G	4
Visit 5 (Day 61)	~140	Anti-Toxin B neutralizing antibodies	1
		Anti-Toxin A neutralizing antibodies	2
		Anti-Toxin B immunoglobulin G	3
		Anti-Toxin A immunoglobulin G	4
Visit 6 (Day 180)	~140	Anti-Toxin B neutralizing antibodies	1
		Anti-Toxin A neutralizing antibodies	2
		Anti-Toxin B immunoglobulin G	3
		Anti-Toxin A immunoglobulin G	4
Visit 7 (Day 390)	~140	Anti-Toxin B neutralizing antibodies	1
		Anti-Toxin A neutralizing antibodies	2
		Anti-Toxin B immunoglobulin G	3
		Anti-Toxin A immunoglobulin G	4
Visit 8 (Day 491)	~60	Anti-Toxin B neutralizing antibodies	1
		Anti-Toxin A neutralizing antibodies	2
		Anti-Toxin B immunoglobulin G	3
		Anti-Toxin A immunoglobulin G	4
Visit 10 (Day 521)	~50	Anti-Toxin B neutralizing antibodies	1
		Anti-Toxin A neutralizing antibodies	2
		Anti-Toxin B immunoglobulin G	3
		Anti-Toxin A immunoglobulin G	4
Visit 11 (Day 670)	~50	Anti-Toxin B neutralizing antibodies	1
		Anti-Toxin A neutralizing antibodies	2
		Anti-Toxin B immunoglobulin G	3
		Anti-Toxin A immunoglobulin G	4

8.8.3 Immunological Correlates of Protection

No generally accepted immunological correlate of protection has been demonstrated so far for the Ag used in the *C. difficile* investigational vaccine.

8.9 Biomarkers

Biomarkers are not evaluated in this study.

8.10 Health Economics or Medical Resource Utilization and Health Economics

Health Economics/Medical Resource Utilization and Health Economics parameters are not evaluated in this study.

8.11 Study Procedures During Special Circumstances

During special circumstances (eg, COVID-19 pandemic), the specific guidance from local public health and other competent authorities regarding the protection of individuals' welfare must be applied. For the duration of such special circumstances, the following measures may be implemented for enrolled subjects:

- Safety follow-up may be made by a telephone call, other means of virtual contact, or home visit, if appropriate.
- Diary cards may be transmitted from and to the site by electronic means and/or conventional mail.
- Biological samples may be collected at a different location* other than the study site or at subject's home. Biological samples should not be collected if they cannot be processed in a timely manner or appropriately stored until the intended use.
- If despite best efforts it is not possible to collect blood samples within the interval predefined in the protocol (see [Table 7](#)), then the interval for blood sampling may be extended up to a maximum length of 30 days before the next blood sampling. Impact on the per protocol set for analysis of immunogenicity will be determined on a case-by-case basis.
- A limited number of subjects may be recruited in addition in the Step 4 in the active arms, should there be a high rate of missed visit and/or visit outside of planned interval and/or withdrawal due to the current exceptional and unpredictable circumstances.

*It is the Investigator's responsibility to identify an alternate location. The Investigator should ensure that this alternate location meets ICH GCP requirements, such as adequate facilities to perform study procedures, appropriate training of the staff and documented delegation of responsibilities in this location. This alternate location should be covered by proper insurance for the conduct of study on subjects by Investigator and staff at a site other than the designated study site. Refer to EMA Guidance on the Management of Clinical Trials during the COVID-19 (Coronavirus) pandemic (Version 4, 04 February 2021) for more details.

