6.6.2 Treatment Allocation to the Subject

Treatment numbers will be allocated by dose.

The enrollment will be performed to ensure equal distribution of the population within the age strata (subjects 18-45 years of age versus subjects 50-70 years of age).

Allocation of the subject to a study group at the study center will be performed using SBIR. As the study will enroll 2 age groups sequentially through 4 steps (Step 1: 18-45 years of age and Steps 2, 3, and 4: 50-70 years of age), the steps will be considered as stratification factors with a specific size and group ratio at each step (Step 1: 20 subjects with ratio 1:1 between CDIFF Ag

and placebo alone; Step 2: 20 subjects with ratio 1:1 between CDIFF Ag and placebo alone, Step 3: 30 subjects with ratio 1:1:1 between CDIFF Ag, CDIFF Ag + AS01_B and placebo; Step 4: 70 subjects with ratio 5:7:2 between CDIFF Ag, CDIFF Ag + AS01_B and placebo). Within the 18-45 years age group, the randomization algorithm will use a minimization procedure accounting for gender (female, male), while within the 50-70 years age group, the randomization algorithm will use a minimization procedure accounting for age (50-59 years of age, 60-70 years of age) and gender (female, male). Minimization factors will have equal weight in the minimization algorithm. A minimum of 20% of each minimization factor category will be required to allow enrolling all categories within each minimization factor (refer to Section 8.11 for study procedures to be considered during special circumstances).

After obtaining the signed or witnessed/thumb printed and dated informed consent form (ICF) from the subject and having checked the eligibility of the subject, the study staff in charge of the vaccine administration will access SBIR. Upon providing the age (subjects 18-45 years of age versus subjects 50-70 years of age), the gender, and the subject identification number, the randomization system will determine the study group and will provide the treatment number to be used for the first dose.

The number of each administered treatment must be recorded in the eCRF on the Vaccine Administration screen.

When SBIR is not available, please refer to the SBIR user guide or the SPM for specific instructions.

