6.6.3 Blinding

Data will be collected in an observer-blind manner. By observer-blind, it is meant that during the course of the study, the vaccine recipient and those responsible for the evaluation of any study endpoint (eg, safety and reactogenicity) will all be unaware of which vaccine was administered. To do so, vaccine preparation and administration will be done by authorized medical personnel who will not participate in any of the study clinical evaluations. The Investigator and the subjects will not have access to the treatment allocation up to Day 390.

The statistical analyses will be performed in 3 steps. Refer to Section 9.8 for controlled unblinding for the first and second interim analysis.

The data for third dose will be collected in a partial blind manner.

After Day 390, only the subjects will remain fully blinded. Those responsible for the evaluation of any study endpoint (eg, safety and reactogenicity) will be partially blinded, as no placebo subjects will be included for Dose 3.

The laboratory in charge of the laboratory testing will be blinded to the treatment, and codes will be used to link the subject and study (without any link to the treatment attributed to the subject) to each sample.

6.6.3.1 *Emergency Unblinding*

Unblinding of a subject's individual treatment code should occur only in the case of a medical emergency when knowledge of the treatment is essential for the clinical management or welfare of the subject.

The emergency unblinding process consists of the automated internet-based system (SBIR) that allows the Investigator to have unrestricted, immediate and direct access to the subject's individual study treatment.

As back-up process, the Investigator has the option of contacting a GSK Helpdesk (refer to [Table 16](#)) if he/she needs support to perform the unblinding (ie, he/she cannot access SBIR).

Non-investigator physician (eg, physician from emergency room) or subject/care giver/family member can also request emergency unblinding either via the Investigator (preferred option) or via the GSK Helpdesk (back-up process). Contact details of Investigator and GSK Helpdesk are reported in the subject card.

Table 16 Contact Information for Emergency Unblinding

GSK Helpdesk
24-hour and 7-day availability
The Helpdesk is available by phone, fax and email
Toll-free number: [name]
[contact]
[contact]
email: [contact]

A subject may continue in the study if that subject's treatment assignment is unblinded.

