9.2 Sample Size Determination

This study is a Phase I safety study to get preliminary safety and immunogenicity assessments of vaccine formulations in adults.

The target will be to enroll a maximum of 140 healthy subjects (approximately 20 subjects aged 18-45 years in Step 1, approximately 20 subjects aged 50-70 years in Step 2, approximately 30 subjects aged 50-70 years in Step 3, and approximately 70 subjects aged 50-70 years in Step 4 [refer to [Table 10](#) and [Figure 1](#)]) (refer to Section [8.11](#) for study procedures to be considered during special circumstances).

The sample size of 45 subjects aged 50-70 years in each active arm (CDIFF Ag or CDIFF Ag + AS01_B) would provide a probability of 80% or 90% to observe at least 1 specific AE, if the true AE rate is 3.5% or 5.0%, respectively, in that group.

[Table 22](#) illustrates the precision on the percentage of subjects with symptoms following vaccination with 45 subjects vaccinated in each active arm.

Table 22 95% Confidence Interval for 1 Proportion with 45 Subjects

Number of Subjects with a Symptom	Percentage	Exact 95% Confidence Interval	
		Lower Limit	Upper Limit
0	0.0%	0.0%	7.9%
1	2.2%	0.1%	11.8%
2	4.4%	0.5%	15.1%
3	6.7%	1.4%	18.3%
4	8.9%	2.5%	21.2%
5	11.1%	3.7%	24.1%
6	13.3%	5.1%	26.8%
7	15.6%	6.5%	29.5%
8	17.8%	8.0%	32.1%
9	20.0%	9.6%	34.6%
10	22.2%	11.2%	37.1%
11	24.4%	12.9%	39.5%
12	26.7%	14.6%	41.9%

Table 22 95% Confidence Interval for 1 Proportion with 45 Subjects

Number of Subjects with a Symptom	Percentage	Exact 95% Confidence Interval	
		Lower Limit	Upper Limit
13	28.9%	16.4%	44.3%
14	31.1%	18.2%	46.6%
15	33.3%	20.0%	49.0%
16	35.6%	21.9%	51.2%
17	37.8%	23.8%	53.5%
18	40.0%	25.7%	55.7%
19	42.2%	27.7%	57.8%
20	44.4%	29.6%	60.0%
21	46.7%	31.7%	62.1%
22	48.9%	33.7%	64.2%
23	51.1%	35.8%	66.3%
24	53.3%	37.9%	68.3%
25	55.6%	40.0%	70.4%
26	57.8%	42.2%	72.3%
27	60.0%	44.3%	74.3%
28	62.2%	46.5%	76.2%
29	64.4%	48.8%	78.1%
30	66.7%	51.0%	80.0%
31	68.9%	53.4%	81.8%
32	71.1%	55.7%	83.6%
33	73.3%	58.1%	85.4%
34	75.6%	60.5%	87.1%
35	77.8%	62.9%	88.8%
36	80.0%	65.4%	90.4%
37	82.2%	67.9%	92.0%
38	84.4%	70.5%	93.5%
39	86.7%	73.2%	94.9%
40	88.9%	75.9%	96.3%
41	91.1%	78.8%	97.5%
42	93.3%	81.7%	98.6%
43	95.6%	84.9%	99.5%
44	97.8%	88.2%	99.9%

Table 22 95% Confidence Interval for 1 Proportion with 45 Subjects

Number of Subjects with a Symptom	Percentage	Exact 95% Confidence Interval	
		Lower Limit	Upper Limit
45	100.0%	92.1%	100.0%

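### Section 8.11 lets Step 4 add subjects to the active arms only, with no allocation, blinding or analysis provision for them

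*Protocol*

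**What the plan says.** Protocol 6.6.2 treats each step as a stratum with its own size and ratio: "Step 4: 70 subjects with ratio 5:7:2 between CDIFF Ag, CDIFF Ag + AS01_B and placebo". That gives 25, 35 and 10 subjects. Section 6.6.3 says that recipients are blinded and that "those responsible for the evaluation of any study endpoint (eg, safety and reactogenicity) will all be unaware of which vaccine was administered". It also keeps the allocation from the Investigator and subjects up to Day 390.

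Section 8.11, repeated in the synopsis, adds a contingency: "A limited number of subjects may be recruited in addition in the Step 4 in the active arms". The trigger is many missed or out-of-window visits, or many withdrawals, as a result of the special circumstances. The section gives no number, threshold, timing, ratio between the two active arms, SBIR procedure or blinding statement. Sections 4.1, 6.6.2 and 9.2 refer to 8.11 but supply none of these either.

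For the analysis, Protocol 9.4.2.1 bases primary safety on the Exposed Set, which is everyone with at least one dose (Protocol 9.3, SAP 5.2). SAP 6.2 presents data by age group and treatment. The COVID-19 Set in SAP 5.6 covers late Day 61 samples only and serves immunogenicity summaries. No flag, separate summary or sensitivity analysis is planned for subjects recruited under 8.11.

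**The concern.** A recruitment wave known to contain no placebo tells those involved that every recruit in it is on active vaccine. The protocol accepts this reasoning elsewhere: sections 4.2.1 and 6.6.3 call the Investigator and evaluators only partially blinded at Dose 3 because no placebo subjects take part. For 8.11 additions it makes no such declaration.

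The primary endpoints include diary-reported solicited symptoms and the Investigator's judgement of whether general symptoms and unsolicited AEs are related. Both can be influenced by knowing that an injection is active. The expected direction is more reporting in the active arms with no change in placebo, although the documents do not prove that direction. Protocol 4.2.2 includes placebo as the control for reactogenicity and safety, so added subjects without concurrent placebo would weaken that control for part of each active arm. Titres are less exposed, because 6.6.3 blinds the laboratory.

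**Working it through.** **1. The plan's own figure.** Section 9.2 takes 45 older adults per active arm and says that this number "would provide a probability of 80% or 90% to observe at least 1 specific AE", at assumed true rates of 3.5% and 5.0%. With P = 1 − (1 − p)^n and n = 45:

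- p = 0.035: 1 − 0.965^45 = 0.799 (stated 80%)
- p = 0.05: 1 − 0.95^45 = 0.901 (stated 90%)

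Both reproduce. Extra active subjects raise these probabilities slightly (n = 52: 84.3% and 93.1%), so the issue is not precision.

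**2. When would active status be inferable?** The documents leave two cases open.

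- *Added after the planned 70 are allocated.* No placebo is being assigned, so active status can be inferred and there is no concurrent placebo. The trigger points this way, since missed visits and withdrawals follow earlier dosing. SAP 5.6 shows that it is realistic: a COVID-19 pause pushed Day 61 visits off schedule.
- *Added while Step 4 is still randomising.* If the additions were mixed in through SBIR, for example by changing the ratio, an individual's status need not be inferable. The ratio would then depart from the stated 5:7:2 by an undocumented route.

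In both cases the choice between the two active formulations stays hidden.

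**3. Size.** Inputs from the documents: 45 older adults per active arm, and 10 placebo among 70 in Step 4. Assumptions made here: the number added; a split of about 5:7 between the active arms; a rise d of 10 to 20 points in the added subjects' reporting of a symptom; otherwise the same underlying rate.

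With a added to an arm: share = a / (45 + a); shift in the pooled percentage = share × d; Step 4 placebo share = 10 / (70 + total added); placebo needed to keep 5:7:2 = total added × 2/12.

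| Added (Ag + Ag/AS01B) | Share of Ag | Share of Ag + AS01B | Shift, Ag (points) | Shift, Ag + AS01B (points) | Step 4 placebo share | Placebo to keep 5:7:2 |
|---|---|---|---|---|---|---|
| 0 | – | – | – | – | 10/70 = 14.3% | – |
| 3 + 4 | 3/48 = 6.3% | 4/49 = 8.2% | 0.6–1.3 | 0.8–1.6 | 10/77 = 13.0% | about 1 |
| 5 + 7 | 5/50 = 10.0% | 7/52 = 13.5% | 1.0–2.0 | 1.3–2.7 | 10/82 = 12.2% | 2 |
| 10 + 14 | 10/55 = 18.2% | 14/59 = 23.7% | 1.8–3.6 | 2.4–4.7 | 10/94 = 10.6% | 4 |

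For 12 added subjects, the largest shift equals 7 × 0.20 = 1.4 subjects out of 52. In Table 22 the 95% interval at 23/45 runs from 35.8% to 66.3%, about 30 points wide.

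**The case against.** The rule is optional and limited, and there is no sign that it was used. Section 9.2 and SAP 3.1 still give 45 per active arm in older adults, and Table 21 shows about 140 subjects up to Day 390 and about 60 at Day 491, which is 25 + 35. These are planned or approximate counts, so they do not settle the question.

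Recruitment is probably over. The rationale for Amendment 03 reports two-dose interim results, and section 9.5 sets that analysis for when all data to Day 61 are available. Changing the allocation rule now may therefore alter nothing. This stands, and it makes the SAP part of the remedy the likelier one to matter.

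The incentive to over-report is also limited. In Step 4, 12 of 14 subjects (86%) receive active vaccine anyway, so knowing it moves expectation only from 86% to 100%. Solicited local reactions are all deemed related (Appendix 6), so causality bias cannot touch them. Section 9.1 tests no hypotheses, and SAP 16 plans no between-group safety comparisons. Placebo is already pooled over Steps 2 to 4 while AS01B appears only in Steps 3 and 4, so control was never fully concurrent. SAP 16.1 tabulates AEs before and during the pandemic, which partly addresses calendar time. All of this limits the size, but none of it supplies an allocation or blinding rule or identifies the added subjects.

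A reader might infer that added subjects are known to be on active vaccine and were never randomised against placebo. The documents do not say so; it depends on the timing in step 2 of the working. A reader might also see a breach of the maximum of 140 in section 9.2, but that sentence itself refers to 8.11, so no separate point arises.

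**Conclusion.** The point holds in conditional form. The active-only rule, the unqualified blinding statement and the unflagged pooling are all in the text. Inferable active status and the lack of concurrent placebo follow only if subjects are added after the planned 70 are allocated, which is plausible but not stated. With 12 added and a 10 to 20 point reporting effect, both assumed, the pooled percentages rise by 1.0 to 2.0 points (CDIFF Ag) and 1.3 to 2.7 points (CDIFF Ag + AS01B). That is small in a descriptive analysis of this size. The documents do not support a conclusion that the safety comparison has in fact been biased. The change is still worth making: the primary endpoints are of the kind that blinding protects, and the remedy is cheap.

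**What to change.** **If Step 4 recruitment is still possible:** in 8.11 and the synopsis, state that any added Step 4 subjects are allocated through SBIR at the existing 5:7:2 ratio including placebo. The cost is one sentence in each place and about one placebo subject per six active (2 for 12).

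**If active-only subjects have already been added:**

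- State how many, and describe them as partially blinded.
- Flag them in the SAP.
- Keep them in the Exposed Set and the primary safety tables. Removing dosed subjects would contradict that set's definition and weaken the main safety display of a first-in-human study.
- Add a sensitivity table of solicited and unsolicited AEs by group without them, and a separate summary of their safety data.
- Leave their place in the immunogenicity analysis unchanged.

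The cost is one flag, one sensitivity table and one short summary. If none were added, one sentence saying so closes the point.
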